Due to the need to establish prevention and treatment schemes in stages prior to diabetes, the timely detection of prediabetes turns out to be one of the best schemes to use. In the diabetes prevention clinic, a prevalence of prediabetes of approximately 17% has been observed in subjects older than 18 years, who have been suggested to change their eating habits and increase their physical activity. However, the current labor and occupational demand is an important barrier in the implementation of a new lifestyle. Until now, drugs have not been an option in the treatment, since it raises the costs and increases the possibility of secondary reactions. In consequence, clinical intervention studies have been implemented based on the oral consumption of curcumin, supported by hundreds of basic and applied research on its benefits in health and diseases related to insulin resistance. Therefore, it is suggested that oral consumption of curcumin in pre-diabetic individuals with insulin resistance may be a good adjuvant that increases insulin sensitivity and improves the adverse metabolic state, characteristic of these patients.

3. Justification

Diabetes is a worldwide disease and recent research point to the importance of predicting its development in previous stages. It has been established that insulin resistance is one of the main factors that intervene in the development of diabetes. However, in these stages it has been noticed that the secretion of insulin by the β cells is increased, so these individuals can maintain the glucose homeostasis at normal levels. In later stages, the progressive decline of the function in the pancreatic β cells, promotes the deterioration of glucose homeostasis and the consequent development of hyperglycemia. This leads to focus on these two routes, to avoid the possible progression to diabetes.

Nowadays, the drugs used usually represent problems of treatment abandonment due to side effects and changes in lifestyle, since the disease manifestations are not evident. Therefore, the inclusion of parallel therapies that increase insulin sensitivity and prevent the deterioration of the β cells in the pancreas at the same time, could be considered as an excellent treatment.

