Since curcumin has the ability to increase insulin sensitivity, improve β -pancreatic function and is considered a safe supplement by the FDA, it has been decided to include therapy based on oral consumption of curcumin in subjects with prediabetes who show resistance to insulin. This scheme will allow to attack metabolically the barriers previously presented, as well as overcome barriers due to the inability to adjust to lifestyle changes.

4. Hypothesis

Oral supplementation with curcumin will increase insulin sensitivity measured through homeostatic model HOMA-Beta and the Matsuda index.

5. Objectives

General: Determine the effects of oral supplementation with curcumin to improve insulin sensitivity through the homeostatic models HOMA β and Matsuda index.

Specifics

- a. Determine the effect curcumin supplementation on the levels of: glucose, insulin (pre- and post-prandial), glycosylated hemoglobin, blood pressure, insulin sensitivity, lipid level (e.g., cholesterol, triglycerides, high and low lipoproteins density) and anthropometric measures (weight, body mass index, waist-hip ratio).
- b. Determine the effect of oral curcumin supplementation on models of insulin resistance measured through HOMA-IR and insulinogenic index.
- c. Determine if the consumption of curcumin supplementation will decrease the levels of inflammation markers: PCR, IL1, IL-6, FNT α .
- d. Determine the safety of curcumin supplementation by measuring the existence of possible side effects.

Methodology

Type and design of the study

It is a randomized, double-blind, placebo-controlled clinical trial.

Population and sample size.

142 pre-diabetic patients will be included, with prior informed consent, according to the criteria of the ADA [6]. The subjects will be randomly assigned to the treatment group with curcumin (n = 71) or the placebo group (control group, n = 71) using a fixed randomization scheme with assignment based on random numbers generated by a computer.

The calculus of the sample was performed with the statistical program Gpower 3.1, which resulted in 71 individuals per group, to obtain a statistical power of 80% in difference of means between two independent samples with an effect size of 0.5 in a two-tailed test, contemplating a 10% of losses during the study period.

Criteria of inclusion, exclusion and elimination.

Inclusion Criteria

- Men and women with age between 18 and 60 years old.
- With prediabetes:
 - a) Fasting serum glucose: 100-125 mg/dL

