- Anthropometric measurements: weight, height, waist circumference, hip circumference, waist-hip circumference ratio and body fat percentage. They will be measured using an electric bio impedance scale and a measuring tape.

- Clinical: It will be determined in the Central Laboratory by standard methods and/or automated equipment, and includes the following:
 - a) Systolic blood pressure and diastolic blood pressure.
 - b) Blood chemistry: insulin, triglycerides, cholesterol, HDL cholesterol, LDL cholesterol, uric acid, creatine, urea, BUN, alanine amino transferase, alkaline phosphatase, glutamyl transferase, lactic dehydrogenase, glycosylated hemoglobin, direct bilirubin, indirect bilirubin, total bilirubin.
 - c) Blood count
 - d) Inflammation markers: PCR, IL 1, IL6, TNF- α .
 - e) Glucose tolerance curve: Fasting serum glucose and at 30, 60, 90 y 120 min after the oral dose of glucose (75 gr).
 - f) Parameters of insulin resistance and sensitivity under the following formulas
 - g) HOMA-IR: $(\text{Insulin } \mu\text{U/ml})(\text{Glucose mg/dl})/405$.
 - h) Matsuda index: $10,000/\sqrt{[(\text{basal glucose})(\text{basal insulin})*(\text{glucose})(\text{insulin})]}$
 - i) Insulinogenic: $\Delta \text{ insulin}/\Delta \text{ glucose}$.
 - j) HOMA1-%B: $(20)(\text{FPI})/(\text{FPG} - 3.5)$

Procedure

Intervention

Participants who meet the inclusion requirements and wish to participate in the study will sign an informed consent. 142 individuals will be included, who will be randomized to receive curcumin (n=71) or placebo (n=71).

- All participants will receive the same diet and exercise indications for a period of three months after enrollment (before randomization).

- Regarding the diet, all patients who enter the research protocol will be assessed and supervised. The feeding plan will be prepared by a nutritionist, individually for each patient, based on the recommendations of the American Diabetes Association 2018, with the following: Carbohydrates 55%, proteins 20% and lipids 25%.

According to the needs of the patient, the quantity of kilocalories/day is calculated. For weight reduction 20 kcal/kg/day, weight maintenance 25 kcal/kg/day. Follow-up appointments will be made by nutrition: at the beginning, 4, 8 and 12 weeks after the start of the intervention.

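### The hypothesis and general objective name HOMA-beta as a measure of insulin sensitivity, although by the plan's own formula it is an insulin-output index, and no favourable direction is stated for it

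*Combined protocol and SAP*

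**What the plan says.** Section 4 (Hypothesis) states: "Oral supplementation with curcumin will increase insulin sensitivity measured through homeostatic model HOMA-Beta and the Matsuda index". The general objective in section 5 likewise aims "to improve insulin sensitivity through the homeostatic models" HOMA-beta and Matsuda. Specific objective b refers to "models of insulin resistance measured through HOMA-IR and insulinogenic index".

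The variable definitions, under the continuous clinical variables, give the formulas. Item f introduces the whole list as indices of resistance and sensitivity, and that list includes the insulinogenic index (item i) and HOMA1-%B (item j). Item j gives HOMA-beta as 20 × FPI / (FPG − 3.5), without a unit for glucose.

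Elsewhere the protocol keeps the two constructs apart:

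- The Background presents HOMA-IR, not HOMA-beta, as the HOMA-based estimate of sensitivity.
- The Justification describes insulin resistance and beta-cell decline, then says: "This leads to focus on these two routes, to avoid the possible progression to diabetes". It calls for therapies that "increase insulin sensitivity and prevent the deterioration of the" beta cells together.
- The last paragraph of the Justification lists two effects: "Since curcumin has the ability to increase insulin sensitivity, improve" beta-cell function.
- The title of reference 10, the HOMA source paper, names insulin resistance and beta-cell function as two outputs.

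The Statistical analysis section makes 2-hour glucose, HOMA-IR, HOMA-beta, Matsuda and the insulinogenic index the primary variables, on which the success of the study is to be judged. It gives no favourable direction for HOMA-beta.

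**The concern.** The main hypothesis assigns HOMA-beta to the wrong construct. Fasting insulin is in the numerator of HOMA-beta and in the denominator of Matsuda. Suppose a participant becomes more sensitive and needs less insulin to hold the same glucose. Matsuda improves and HOMA-beta falls. On the natural reading of the hypothesis, the fall in HOMA-beta is evidence against it. Conversely, a rise in HOMA-beta caused by worsening resistance and compensatory insulin output would read as support. This matters in this population, because the Justification says that "in these stages it has been noticed that the secretion of insulin by the" beta cells is already raised at this stage.

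Objective b has a related label: it treats the insulinogenic index as a resistance model. No section says what that index measures, but its formula, change in insulin over change in glucose, describes an insulin response.

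At stake is how the trial's main conclusion is read. If the label is corrected only after the randomisation keys are opened, the correction will look chosen to suit the results.

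**Working it through.** The plan gives no expected value or change for any of these indices, so there is no figure of its own to reproduce. The check applies its formulas.

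**Inputs from the variable definitions**
- HOMA-beta = 20 × I0 / (G0 − 3.5) (item j)
- Matsuda = 10,000 / √(G0 × I0 × G × I) (item h). The second pair is read as the glucose-tolerance (OGTT) values; the item does not say whether they are means.
- HOMA-IR = I0 × G0 / 405 (item g)

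**Assumptions**
- Insulin changes of 10, 20 and 30%. The percentage results do not depend on baseline insulin.
- Fasting glucose 110 mg/dL, within the 100–125 mg/dL inclusion range.
- Glucose in item j in mmol/L, as the Background defines FPG, at 18 mg/dL per mmol/L. The constant 3.5 is then 63 mg/dL.

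**Step 1: glucose unchanged, insulin multiplied by s.** HOMA-beta and HOMA-IR scale by s. Matsuda scales by 1/s if fasting and OGTT insulin move alike, and by 1/√s if only fasting insulin moves. Neither the unit nor the baseline glucose matters here, provided that glucose exceeds the constant.

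| Insulin | HOMA-beta | HOMA-IR | Matsuda, all insulin | Matsuda, fasting only |
|---|---|---|---|---|
| −10% | −10% | −10% | +11.1% | +5.4% |
| −20% | −20% | −20% | +25.0% | +11.8% |
| −30% | −30% | −30% | +42.9% | +19.5% |
| +10% | +10% | +10% | −9.1% | −4.7% |
| +20% | +20% | +20% | −16.7% | −8.7% |
| +30% | +30% | +30% | −23.1% | −12.3% |

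**Step 2: insulin falls and fasting glucose falls too.** HOMA-beta changes by the factor s × (110 − 63) / (G1 − 63). It avoids falling only if the glucose drop is at least (1 − s) × 47 mg/dL:
- insulin −10%: 0.1 × 47 = 4.7 mg/dL
- insulin −20%: 0.2 × 47 = 9.4 mg/dL
- insulin −30%: 0.3 × 47 = 14.1 mg/dL

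For the 20% case, the threshold runs from 0.2 × 37 = 7.4 mg/dL at a start of 100 to 0.2 × 62 = 12.4 mg/dL at a start of 125.

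Example below the threshold: glucose 110 to 105, all insulin −20%, OGTT glucose fixed. HOMA-beta: 0.8 × 47/42 = 0.895, a fall of 10.5%. Matsuda: 1 / (0.8 × √(105/110)) = 1.279, a rise of 27.9%.

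**Step 3: insulin rises.** HOMA-beta rises unless fasting glucose rises enough to offset it. With fasting and OGTT insulin up alike and OGTT glucose fixed, Matsuda improves only if fasting glucose drops by more than 110 × (1 − 1/s²):
- insulin +10%: 19.1 mg/dL
- insulin +20%: 33.6 mg/dL
- insulin +30%: 44.9 mg/dL

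If OGTT glucose falls in proportion, or only fasting insulin rises, the threshold is 110 × (1 − 1/s) = 10.0, 18.3 and 25.4 mg/dL.

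**Step 4: a case of agreement.** Insulin unchanged, fasting glucose 110 to 100, OGTT glucose fixed. HOMA-beta: 47/37 = 1.270, a rise of 27.0%. Matsuda: √(110/100) = 1.049, a rise of 4.9%.

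**Unit.** If glucose in item j were entered in mg/dL, the 20% threshold in step 2 would be 0.2 × 106.5 = 21.3 mg/dL. The signs in step 1 would not change.

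**The case against.** Opposite movement is not a defect in itself. HOMA-IR and Matsuda also move in opposite directions by construction, and nobody is misled because their favourable directions are understood. That is right. The defect is the construct label together with the missing direction for HOMA-beta.

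A reader might infer that HOMA-beta and Matsuda must always conflict. The documents do not support that. Both rise when fasting glucose falls at steady insulin, and a 10% insulin fall needs only a 4.7 mg/dL glucose drop to be offset. All participants receive diet and exercise advice. The animal work cited in the Background reports higher secretion together with lower glycaemia and lower HOMA-IR, a pattern in which the indices could agree.

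A reader might also infer that the plan expressly counts any HOMA-beta rise as success. It does not. That is the natural reading of the hypothesis, but no section states it.

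Finally, the analysis is the same whatever the label: HOMA-IR, HOMA-beta and Matsuda are all primary, and each is compared by t test and ANCOVA. This limits the consequence to interpretation. It does not remove it, because the hypothesis still names HOMA-beta for sensitivity while HOMA-IR is left to objective b.

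**Conclusion.** The point holds as an internal inconsistency in the main hypothesis and should be fixed. HOMA-beta is called a sensitivity measure in the hypothesis, the general objective and the item f heading, against the plan's own formula and rationale. At unchanged glucose, a 20% insulin fall lowers HOMA-beta by 20% and raises Matsuda by 11.8% to 25.0%. These signs follow from the formulas alone. The glucose thresholds for agreement rest on the assumed 110 mg/dL, the assumed insulin changes and the mmol/L reading.

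How often the indices would disagree in this trial cannot be derived from the documents. Nor do they support the inference that the trial cannot test insulin sensitivity: Matsuda and HOMA-IR are both planned as primary variables. The harm is a contradictory or misread conclusion, with no loss of data or power.

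**What to change.** Before the randomisation keys are opened:

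1. In the hypothesis and general objective, remove HOMA-beta as a sensitivity measure. Use the Matsuda index (higher is better) with HOMA-IR (lower is better).
2. In objective b, place HOMA-beta beside the insulinogenic index and describe both as beta-cell or insulin-response measures.
3. In the Statistical analysis section, add a sentence that these two indices do not count for or against the sensitivity hypothesis.
4. If the sponsor prefers to keep beta-cell function in the hypothesis, in line with the Justification, make it a separate claim. State in advance which direction of HOMA-beta counts as improvement, and read it alongside Matsuda, because HOMA-beta also rises when resistance raises insulin.
5. Reword the item f heading to cover both sensitivity/resistance and beta-cell function, and state the glucose unit in item j.

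The cost is a few lines of text. All the indices are already planned, so no new patients, tests or models are needed. How the five primary variables combine into a verdict on the study is a separate issue that this change does not settle.

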Chuengsamarn Set al, studied the effects of curcuminoids in the reduction of atherogenic risk in patients with diabetes mellitus type 2 (n = 213), with doses of 1.5 gr per day of curcuminoids, finding side effects in less than 1% of the sample, with a mean of 6-month follow-up, finding that intervention with curcumin significantly reduces pulse wave velocity, increases serum adiponectin levels and decreases leptin levels. As well as decrease in levels of triglycerides, visceral fat and total body fat (15).

Although follow-ups in similar studies with prediabetes have been performed at 6 months, finding significant differences, there are studies with 1 to 3 months follow-ups in obese patients or in metabolic syndrome, where significant differences have been found in lipid levels, bodyweight and inflammation markers. This is why, it is interesting to value the response of curcumin supplementation in less than 6 months, betting on a positive effect on insulin sensitivity after 3 months of intervention.

It has been noticed that the side effect of curcumin have not been reported when consumption is less than 12 g per day. At higher doses there may be presence of nausea and diarrhea. Without finding side effects when curcuminoids were used at doses of 1 to 1.5

g / day (15, 26, 27), this means that the 500 mg dose/12hrs is safe for curcumin supplementation.

2. Problem Statement

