 - b) Glycosylated hemoglobin (HbA1c): 5.7-6.4%
 - c) Post-prandial glucose: 140-199 mg/dL after an oral dose of 75 g of glucose.

Exclusion Criteria

- Subjects with any type of diabetes.
- Subjects with body mass index ≥ 35 kg/m²
- Pregnant Women.
- Volunteers who ingest drugs that alter blood glucose levels, antiplatelet agents, angiotensin-converting enzyme inhibitors, angiotensin II receptor antagonists, fibrates, statins.
- Subjects with serum creatinine > 2 mg/dL or in renal replacement therapy.
- Subjects that normally consume food supplements.
- subjects with acute infections or with chronic diseases (cancer, rheumatoid arthritis, etc.).

Elimination Criteria

- Patients that abandon treatment.
- Subjects that manifest any side effect (nauseas, diarrhea).
- Subjects that during the trial, show Diabetes mellitus diagnosis according to the ADA.

Definition of the variables to be evaluated and how to measure them

Nominals: Each variable is categorized and assigned a level (0 or 1) according to the information obtained in the questionnaires and the clinical results.

- Gender: Male (0) or Female (1)
- Treatment: placebo (0) or curcumin (1)
- Attachment to treatment: no (0), yes (1)
- Altered fasting glucose: no (0), yes (1)

Ordinals

- Body mass index. Is determined by measuring the weight (kg) and the size (m). It will be obtained dividing the weight by the squared size. It will consist of 5 levels: low weight (IMC <19), adequate weight (IMC: 19-24.9), overweight (IMC: 25-29.9), obese (IMC: 30-35), morbid obese (IMC >35).
- HbA1c. It will be determined in automatic equipment from a blood sample-EDTA in the central laboratory. Levels: low (<5.7), medium (5.8-6.4), high (>6.4).
- Fasting glucose and post-prandial glucose. It will be determined by evaluating the glucose tolerance curve after an oral dose of 75g of glucose. Every 30 min, for 2 hours, a peripheral blood sample will be obtained and the glucose concentration will be determined by automated equipment (Central Laboratory). The levels are the following:
Fasting Glucose (mg/dL): normal (<100), prediabetes (100-125), diabetes (>125).
Post-prandial Glucose (mg/dL) (2 horas): normal (<140), prediabetes (140-199), diabetes (>199).

Discontinue: Age, according to the given in the questionnaire.

Continues:

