To achieve the goals of the study and the correct analysis of the data, the variables will be divided into two groups, with the primary ones being expected to be modified by the treatment in the first term, which will define the success or failure of the study. It is expected that the secondary variables may or may not be affected by the treatment. In addition, possible confounders that interfere with the response will be included in the analysis.

- *Primary variables:* post-prandial glucose (2 horas), HOMA-IR, HOMA-β, Matsuda index and insulinogenic.
- *Secondary Variables:* anthropometric measurements, serum lipids, each determination of blood chemistry.
- *Potential confounders:* age and gender.

To determine the statistical difference in the categorical variables between the group of curcumin and placebo, X² will be used. The continuous variables at the beginning and at the end between the two groups will be compared using t student test of independent samples and an analysis of covariance (ANCOVA), which will be adjusted by the initial values of the primary and secondary variables of interest. In addition, the percentage differences between the groups in the values of the primary variables will be analyzed, using values of adjusted covariates (including age, gender, BMI) such as 100 x (curcumin group-placebo group) / placebo group of each study variable.

Table 2. Activities to be carried out during the study period.

Activity	1 st Semester	2 nd Semester	3 rd Semester	Last bimester
Selection and recruitment of patients	→			
Intervention	→			
Anthropometric, clinical and biochemical determinations (markers of stress and inflammation)	→			
Opening of randomization keys			↓	→
Analysis and captured of results			→	
Results publication				→

Ethical and biosecurity aspects

During the development of the project, all determinations and processes will be carried out under the norms and statutes pre-established, dictated by the Ethics and Biosafety Committee of this Hospital. The potential risks of the intervention will be made known to the volunteers before the intervention, which include:

- a) From the sample taking. In each measurement period (initial, intermediate and final) blood sampling is required, which comprises approximately 60 ml, with the risks inherent to blood collection such as bruising and the elimination of contagion risk due to the use of disposable plastic material, new in each subject and in each shot.

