- b) Of the intervention. According to the FDA, there have been no reported adverse reactions to the consumption of curcumin less than 12 g per day. At higher doses there may be presence of nausea and diarrhea. This protocol includes the consumption of 1 g per day and no adverse reactions have been reported, however, an instrument sheet of adverse reactions will be granted and the participants will be instructed to stop treatment if they face any secondary reactions such as nausea, dizziness, vomiting and/or diarrhea.

Relevance and expectations

In the case that treatment is positive, safe alternatives for prediabetes can be established. In addition, derived from the results, an article will be published in a high impact magazine and presented at a congress.

Available resources

We count with the human resources required for the proper development of the project. Within the research group are [name] [name], Resident doctor in the third year of the Internal Medicine specialty at the General Hospital of Mexico and student of a master's degree in Medical Sciences at the UNAM, and [name] [name], Health Sciences Chief department at UAM-Lerma, who has extensive experience in the design of studies and with the necessary facilities for the processing of samples.

A professional in nutrition will be hired, who will be in charge of supervising the food plan during the intervention.

Regarding the material resources, curcumin and placebo capsules are available for patients and the necessary material for the processing of samples for the determination of markers of oxidative stress and inflammation.

Resources to request

The necessary for the glucose tolerance curve: trutol, catheters, syringes, gauze, three-way stopcocks, test tubes for blood collection, enzymatic assay for insulin determination and laboratory tests.

Bibliographic references

1. Diabetes FId. FID, Federación Internacional de Diabetes, 2017. Atlas de la diabetes 2017 [Available from: <http://www.idf.org/diabetesatlas>
3. 2. Classification and Diagnosis of Diabetes: Standards of Medical Care in Diabetes-2018. *Diabetes Care.* 2018;41(Suppl 1):S13-s27.

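### The side-effect objective has no stated analysis, and the elimination rule can remove every affected participant from the groups compared

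*Combined protocol and SAP*

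**What the plan says.** Objectives, Specifics, item d sets the aim: "Determine the safety of curcumin supplementation by measuring the existence of possible side effects".

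Three other parts of the document bear on it:

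- **Elimination Criteria.** Two entries matter: "Subjects that manifest any side effect (nauseas, diarrhea") and "Patients that abandon treatment". The document does not say whether elimination means leaving treatment, follow-up, analysis or all three.
- **Ethical and biosecurity aspects, item b.** Reactions are to be captured: "an instrument sheet of adverse reactions will be granted and the participants will be instructed to stop treatment if they face any secondary reactions". Someone who follows that instruction may meet both elimination criteria.
- **Statistical analysis.** The secondary variables are "anthropometric measurements, serum lipids, each determination of blood chemistry". Side effects are in neither the primary nor the secondary list, nor among the nominal variables defined earlier. Continuous variables are compared between groups at the beginning and the end, by t test and baseline-adjusted ANCOVA.

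The blood chemistry includes "alanine amino transferase, alkaline phosphatase, glutamyl transferase", bilirubins and kidney markers. Table 1 schedules the biochemical and clinical variables at the initial, intermediate (week 6) and final (week 12) visits.

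**The concern.** A stated rule works against a stated objective. The people whose experience answers objective d are the people the elimination rule takes out, and nothing in the document puts them back for a safety count. The recording sheet shows that the information will exist, but the analysis section never uses it.

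The laboratory data do not fill the gap. Harm to the liver or kidney may appear as a large change in a few people, and a comparison of means is poorly suited to finding that. Participants eliminated for a reaction may also be missing from this comparison.

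A safety statement is foreseeable: the Background already describes the dose as safe, and the section on relevance and expectations anticipates safe alternatives for prediabetes if the result is positive. Such a statement would rest on groups from which affected participants may have been removed.

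**Working it through.** **1. Sample size, to fix the denominators.** Inputs from Population and sample size: effect size 0.5, two-tailed, 80% power, 10% losses. Alpha is not stated; 0.05 is assumed. The two-sample t test needs 63.8, so 64 per arm. Allowing for losses, 64 × 1.1 = 70.4, rounded up to 71 (or 64 / 0.9 = 71.1). The stated 71 per group reproduces. Below, 71 is the number randomised and 64 the number evaluable per arm.

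**2. Effect of elimination on the side-effect count.** The document gives no expected rates for this trial. Take 10% on curcumin and 1% on placebo as an assumed illustration.

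| | Curcumin | Placebo |
|---|---|---|
| Events if all 71 are counted | 71 × 0.10 ≈ 7 | 71 × 0.01 ≈ 1 |
| Analysed if affected participants are removed | 71 × 0.90 ≈ 64 | 71 × 0.99 ≈ 70 |
| Side effects among those analysed | 0 | 0 |

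The last row is zero for any pair of rates, because being free of side effects is then the condition for being analysed.

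**3. What full counting could show.** With zero events in n, the exact two-sided 95% upper limit is 1 − 0.025^(1/n). For n = 71 this is 5.1%. The chance of at least one event among 71 is 1 − (1 − p)^71: 51% at a true rate of 1%, 76% at 2% and 97% at 5%.

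**4. Laboratory tests compared as means.** Assumed inputs, not in the documents: alanine aminotransferase log-normal with mean 30 and SD 15 U/L, 64 per arm, and k curcumin participants at 200 or 400 U/L at the end. Share of 20,000 simulated trials with t test p < 0.05:

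| k | at 200 U/L | at 400 U/L |
|---|---|---|
| 1 | 4% | 0.6% |
| 2 | 8% | 2% |
| 3 | 18–19% | 14% |
| 5 | 62% | 91% |

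A hand check shows why three rises are missed. Three participants at 200 raise the arm mean by 3 × 170 / 64 = 7.97 U/L. They also raise that arm's variance to about (3/64)(61/64) × 170² + (61/64) × 15² = 1,506, or 1,530 with the sample correction 64/63. The standard error of the difference is then √((1,530 + 225)/64) = 5.24, and 7.97 / 5.24 = 1.52, short of about 1.98. The outliers inflate the noise along with the signal.

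A second simulation with other assumptions (mean 28, SD 14, upper limit of normal 40 U/L, 71 per arm, rises to 3 to 4.5 times that limit) gives 5%, 8%, 17% and 30% for one to four affected participants. In that simulation a uniform rise of 7 U/L (0.5 SD) in everyone is detected in 84% of trials.

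**5. Unused time point.** Table 1 collects chemistry at week 6, but the analysis compares only the beginning and the end. A rise at week 6 that resolves by week 12 enters no stated analysis.

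**The case against.** The strongest reply is that elimination is never defined as removal from a side-effect tally. A side effect is itself a reason for elimination, so listing eliminations by arm would be one way to measure side effects, and the adverse-reaction sheet is the collection tool for objective d. On this view the defect is missing analysis text. That is right as far as it goes, and it rules out a stronger reading: a reader might infer that the plan would report curcumin as safe whether or not it is. The documents do not support that, because they contain no rule for declaring safety and do not say that recorded reactions will be discarded. What remains is that no passage keeps eliminated participants in any count.

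A reader might also fault the chi-square test, since the section says "To determine the statistical difference in the categorical variables between the group of curcumin and placebo, X² will be used" and the Background cites a trial "finding side effects in less than 1% of the sample". The plan does not assign chi-square to side effects, so this is not an error in the plan. Nor would changing the test help to find harm: for 4/71 against 0/71, uncorrected chi-square gives p = 0.042 and Fisher's exact test 0.120, so the exact test is the less ready to flag a difference.

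On the laboratory side, objective d names side effects only, blood chemistry is not designated a safety measure, and the simulation inputs are chosen. This limits the point to rises in very few people; about five outliers, or a broad shift, would probably be detected.

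**Conclusion.** The concern holds in a bounded form. Objective d has no specified analysis. If eliminated participants leave the analysed set, the side-effect count there is zero in both arms by construction, and the plan is biased toward finding no harm. That consequence depends on how elimination is read, which the document leaves open.

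The laboratory point is secondary and conditional. On the assumed inputs for alanine aminotransferase, one to three large individual rises are detected in about 1% to 19% of trials. The simulations cover the t test, not the ANCOVA. The unused week-6 chemistry follows from the text without assumptions.

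The 5.1% limit for zero events in 71 belongs to any trial of this size. It is not a fault in the plan, but it limits what any safety statement can claim. The change should be made, and the elimination rule's effect on analysis should be settled before the randomisation keys are opened. Bias in the efficacy results from the same rule is a separate matter.

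**What to change.** Add to the nominal variables: *side effect: no (0), yes (1)*.

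Add to the Statistical analysis section: *Safety is analysed in all randomised participants who took at least one capsule, by arm, including those who meet an elimination criterion. The number with any side effect recorded on the adverse-reaction sheet, and the number who stopped because of one, is reported per arm with exact 95% confidence intervals for each rate. For liver and kidney chemistry, the number per arm with a value within the laboratory's reference limits at week 0 and beyond them at any available week 6 or 12 measurement is also reported.*

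State beside it that zero events in 71 would exclude only rates above about 5% (exact two-sided 95% limit 5.1%).

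This concerns analysis only and leaves the rules for stopping treatment as they are. It costs wording and two tables, and the safety statement becomes less favourable than a bare report of no events. The recorded reactions of eliminated participants must be kept. Their later chemistry may be missing, because the document does not say that they return for the week 6 and 12 visits; the number without a later value should be shown by arm.
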